10.3. Lost to Follow-Up

A participant will be considered lost to follow-up if he or she fails to return for scheduled visits and is unable to be contacted by the study site staff. The following actions must be taken if a participant fails to return to the clinic for a required study visit:

- 1. The site will attempt to contact the participant and reschedule the missed visit and counsel the participant on the importance of maintaining the assigned visit and ascertain if the participant wishes to and/or should continue in the study.
- 2. Before a participant is deemed lost to follow-up, the investigator or designee will make every effort to regain contact with the participant (where possible, 3 telephone

calls and, if necessary, a certified letter to the participant's last known mailing address or local equivalent methods). These contact attempts should be documented in the participant's medical record or study file.

Should the participant continue to be unreachable, he or she will be considered to have withdrawn from the study with a primary reason of lost to follow-up.

11. STATISTICAL ANALYSIS

11.1. Sample Size Considerations

This is a feasibility study and accordingly there is not a pre-specified null hypothesis to be tested against for the study endpoints. Data collected from this study will provide preliminary device safety and effectiveness data for the use of the EchoMark/EchoSure System in patients receiving arteriovenous fistulae for hemodialysis access. Descriptive statistics will be reported for the study data. Inferential statistical analysis will be conducted in an exploratory manner. The sample size for this study is planned to be up to 20 subjects at up to 4 investigational sites, with data points collected at multiple timepoints for each subject.

Statistical methods for the study are outlined below.

11.2. Data Analysis Plan

11.2.1 General Principles

All statistical analyses will be performed using Statistical Analysis System (SAS) for Windows (version 9.4, SAS Institute Inc. Cary, NC), STATA (version 16, StataCorp, College Station, TX) or other widely accepted statistical or graphical software. All statistical analysis will be conducted by an independent statistician.

Descriptive statistics will be used to present the data and to summarize results. Discrete variables will be presented using frequency distributions and cross tabulations. Continuous variables will be summarized by presenting the number of observations (N), mean, standard deviation, median, minimum, and maximum values. In general, data for all study subjects combined will be presented. The primary analysis for all baseline characteristics and study outcomes will include all available data for all enrolled subjects. Individual data will be presented in subject listings.

Summaries of the following endpoints present the number and percentage of unique subjects within an event, unless specified otherwise: protocol deviations; subject status; adverse events. Thus, multiple occurrences of the same event are counted only once per subject, unless specified otherwise.

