5.3 End of Study

All enrolled subjects will exit the study when all study related activities and visits are completed, but no later than 24 months.

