- Limited DUS scan performed at the site of EchoMark to determine EchoMark visibility including:
 - 1 BMode, transverse view of EchoMark at center
 - 1 BMode, transverse view of EchoMark at distal edge
 - 1 BMode, Transverse view of EchoMark at proximal edge
 - 1 BMode, Longitudinal view centered over vessel showing full length of EchoMark.
- A duplex exam of the fistula from the EchoMark location and beyond to assess for the presence of stenotic lesions or a fluid collection. If a lesion is present, capture and save an image showing a longitudinal view of the fistula segment with the stenosis, note the location of the stenosis in relation to the anastomosis and EchoMark, and track the stenosis as an adverse event. If a fluid collection is present, capture and save an image noting the location from the anastomosis and the size and volume.
- A duplex scan of the brachial artery to assess flow and diameter, capture a PW image showing the flow and diameter measurements.

7.9 15 Month, 18 Month, and 24 Month (+ 15 Days) Follow-up

All subjects who are willing to reconsent to longer-term follow-up will have a follow-up visit at 15 months, 18 months, and 24 months after baseline procedure. Follow-up visits will include a captures of medical history since the last visit, Duplex scan, and adverse event monitoring. The Duplex scans will include:

- Limited DUS scan performed at the site of EchoMark to determine EchoMark visibility including:
 - 1 BMode, transverse view of EchoMark at center
 - 1 BMode, transverse view of EchoMark at distal edge
 - o 1 BMode, Transverse view of EchoMark at proximal edge
 - 1 BMode, Longitudinal view centered over vessel showing full length of EchoMark
- A duplex exam of the fistula from the EchoMark location and beyond to assess for the presence of a fluid collection. If a fluid collection is present, capture and save an image noting the location from the anastomosis and the size and volume.

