7.11 Fistula Failure

If the subject's fistula is deemed a failure and abandoned by the investigator, a fistula failure case report form will be completed recording the reasoning for the failure. The subject will remain in the study and receive monthly telephone calls to monitor for adverse events and physical assessments of the EchoMark at all standard of care visits. The subject will complete the 180-day and 12 months visit as scheduled to undergo a physical exam, medical history review, adverse event monitoring, and duplex examination of the EchoMark and exit the study.

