7.12 EchoMark Explantation

If the EchoMark is removed, the subject will be followed until the event is resolved. A case report form will be completed to track the reasoning, procedure details, and outcomes. The subject will be monitored with the institution's standard of care, including physical exam and possibly ultrasound. The event will be tracked until the symptoms are resolved and the subject will exit the study.

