9.5 Event Assessment and Follow-Up

The occurrence of an adverse event (AE) or serious adverse event (SAE) may come to the attention of study personnel during study visits and interviews of a study participant presenting for medical care, or upon review by a study monitor.

All AEs including local and systemic reactions not meeting the criteria for SAEs will be captured on the appropriate case report form (CRF). Information to be collected includes event description, time of onset, clinician's assessment of severity, relationship to study product, and time of resolution/stabilization of the event. All AEs occurring while on study must be documented appropriately regardless of relationship. All AEs will be followed to adequate resolution.

Any medical condition that is present at the time that the participant is screened will be considered as baseline and not reported as an AE. However, if the study participant's condition deteriorates at any time during the study, it will be recorded as an AE.

Changes in the severity of an AE will be documented to allow an assessment of the duration of the event at each level of severity to be performed. AEs characterized as intermittent require documentation of onset and duration of each episode.

Investigators will record all reportable events with start dates occurring any time after informed consent is obtained until 7 (for non-serious AEs) or 30 days (for SAEs) after the last day of study participation. At study visits, the investigator will inquire about the occurrence of AE/SAEs since the last visit. Events will be followed for outcome information until resolution or stabilization.

The Investigator is to report all SAEs to the study sponsor within 24 hours of first recognition of the event. Additionally, any device malfunctions, failures, and/or explants are to be reported to the sponsor within 24 hours of first recognition of the event.

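### The general adverse-event summary in 11.2.1 has no time window, although follow-up after month 12 depends on reconsent, so its percentages are neither 12- nor 24-month risks

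*Combined protocol and SAP*

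**What the plan says.** **The summary.** Section 11.2.1 states: "Summaries of the following endpoints present the number and percentage of unique subjects within an event, unless specified otherwise: protocol deviations; subject status; adverse events". A subject with the same event twice counts once. On the data to be used, the section says: "The primary analysis for all baseline characteristics and study outcomes will include all available data for all enrolled subjects". It gives no time window, person-time or censoring rule. Section 11.2.10 does not impute missing values and is silent on unequal follow-up.

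**Who is observed, and for how long.**
- Section 7.9: "All subjects who are willing to reconsent to longer-term follow-up will have a follow-up visit at 15 months, 18 months, and 24 months".
- Section 7.11, failed fistula: "The subject will complete the 180-day and 12 months visit as scheduled to undergo a physical exam". The sentence ends with "duplex examination of the EchoMark and exit the study".
- Section 7.12, explantation: "The event will be tracked until the symptoms are resolved and the subject will exit the study".
- Section 9.5: "Investigators will record all reportable events with start dates occurring any time after informed consent is obtained until 7" days (non-serious) or 30 days (serious) after the last day of participation. Each subject's recording period therefore depends on that subject's own exit.
- Section 5.3 caps participation at 24 months.

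**What is looked for.** Table 1 (Schedule of Events) ends the physical examination, external EchoMark measurement and cannulation log at 12 months. Sections 7.6 to 7.8 and 7.10 require a search for stenosis and have any stenosis tracked as an adverse event. Section 7.9 lists a search for fluid collection only. One sentence of the Protocol Summary does mention a physical examination at the late visits; I rely on Table 1 and 7.9, which agree.

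**What does have a time limit.** The major adverse event composites are set at 30 days (4.2.1, 11.2.6) and 12 months (11.2.8.11). The listed events in 11.2.8.10 run to 12 months, or 4 months for inability to use EchoSure, and are counts of events.

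**The concern.** A percentage of subjects with an event can be read only against a period of observation. Applied as written, the rule puts into one figure subjects watched for less than 12 months (explants), for 12 months (no reconsent, or failed fistula under 7.11) and for 24 months (reconsented). A subject who does not reconsent counts as event-free in months when nobody looked.

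The device is a bioresorbable implant, section 8 reports infection and seroma in earlier use, and the late visits look for fluid collections. Late events are what the extension can reveal, and this is the only planned adverse-event percentage that reaches past month 12. At stake is whether a reader can tell a low late event rate from low late follow-up.

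**Working it through.** The documents state no adverse-event rate, reconsent rate or explant rate, so there is no planned figure to reproduce. What follows is an illustration.

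**Inputs**
- N = 20: planned maximum, section 11.1, roll-ins excluded.
- f = 15% failed fistulas (3 of 20), exit at 12 months: assumed. The prior-cohort table in section 3.5 gives 11.8% and 16.7%.
- e = 5% explanted (1 of 20), exit at 6 months: assumed.
- 12-month risk p12 = 20%, with 10% and 30% as alternatives: assumed.
- Reconsent rate r among the remaining 80%, from 0 to 100%: assumed.
- Constant hazard and equal detection throughout: assumed.

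**Cumulative risks at p12 = 20%**
- p6 = 1 − √0.80 = 0.106
- p24 = 1 − 0.80² = 0.36

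**Expected pooled percentage** = e·p6 + f·p12 + (1 − e − f)·[r·p24 + (1 − r)·p12]
- r = 0: 0.05 × 0.106 + 0.15 × 0.20 + 0.80 × 0.20 = 19.5%
- r = 25%, 50%, 75%: 22.7%, 25.9%, 29.1%
- r = 100%: 0.05 × 0.106 + 0.15 × 0.20 + 0.80 × 0.36 = 32.3%

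In 20 subjects that is about 3.9 against 6.5 with an event, at the same underlying hazard. At p12 = 10% (24-month risk 19%) the range is 9.8% to 17.0%. At p12 = 30% (24-month risk 51%) it is 29.3% to 46.1%. The pooled figure stays below the 24-month risk even at full reconsent, because failed and explanted subjects have left.

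**Person-years**, ignoring other dropout: 1 × 0.5 + 3 × 1 + 16 × (1 + r), which is 19.5 at r = 0 and 35.5 at r = 100% for the same 20 subjects.

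**Sensitivity to late detection.** The spread at p12 = 20% is 0.80 × (0.36 − 0.20) = 12.8 points. It assumes late events are found as readily as early ones, which the thinner late visits make doubtful. If no late event were recorded, the figure would be 19.5% at every reconsent rate. The realistic spread lies between 0 and 12.8 points under the other assumptions.

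**An event that starts only after month 12.** With a true risk of 20% and no early exits, the pooled figure is 20% × r, so 10% at 50% reconsent.

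**After a split at day 365.** Under the same assumptions the first-period crude percentage is 19.5% whatever the reconsent rate. The 0.5-point shortfall from 20% comes from the early explant. For the late period with no events seen, the one-sided 95% upper bound 1 − 0.05^(1/n) is 17.1% for n = 16, 31.2% for n = 8 and 45.1% for n = 5. A late table with its own denominator shows that uncertainty; a pooled figure hides it.

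**The case against.** The strongest reply is that the target is narrow. Every named safety outcome is time-bounded. The sentence in 11.2.1 is a counting convention, and a single pooled table is inferred from its silence on time. The study is small and descriptive, individual listings would let a reader recover event timing, and 11.2.2 already reports completion and reasons for discontinuation.

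Much of this stands and limits the point. Listings and disposition tables help, but they do not define the percentage, and 11.2.2 does not ask for reconsent counts. A descriptive percentage still needs a stated period and denominator.

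Four stronger readings are tempting and not supported:
- *That the trial's safety results in general lack a time limit.* The 30-day and 12-month composites and the listed counts do not.
- *That the request for a pivotal trial rests on the affected figure.* Section 4.2.1 ties that request to the close of the 90-day visit window.
- *That coverage of months 0 to 12 is complete and only the later period is selective.* Explanted subjects may exit well before month 12.
- *That subjects followed late are by rule those with a working fistula.* Section 7.11 has failed-fistula subjects exit at 12 months, but 7.9 opens the late visits to every subject willing to reconsent, and the Protocol Summary schedules all implanted subjects to 24 months while also giving enrollment as up to 365 days. These sections conflict.

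**Conclusion.** The point holds for the general adverse-event summary in 11.2.1 and for nothing wider. As written, it yields a percentage that is neither a 12- nor a 24-month risk and that varies with the reconsent rate whenever late events are recorded. That conclusion follows from the text of 11.2.1, 7.9, 7.11, 7.12 and 9.5 and needs no assumed rate.

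The size does rest on assumptions. The range of 19.5% to 32.3%, against a 24-month risk of 36%, depends on the hazard, exit shares and equal detection listed above, and is best read as the upper end of what reconsent alone could do in that scenario. This is a reporting defect that should be corrected before the adverse-event tables are produced.

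**What to change.** In 11.2.1, define two non-overlapping periods by event onset date:

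1. **Implantation through day 365, all implanted subjects.** Show the number followed to day 365 and note explants and other exits before then. List events between consent and implantation separately. Naming implanted subjects also settles the difference between 11.2.1, which says enrolled (defined in 11.2.2 by signed consent), and 11.2.4, which requires successful implantation.
2. **Day 366 to exit.** The denominator is subjects who reconsented and were seen after day 365. Beside it, show how many were not followed, with fistula and device status at their last visit.

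Use day 365 as the cut, not the 12-month visit: that visit has a ±15-day window, so a cut at the visit would leave gaps or overlaps. List separately any event after day 365 in a subject who did not reconsent, such as a serious event caught by the 30-day post-exit rule in 9.5. State in a footnote that ascertainment differs between the two periods.

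Reconcile the Protocol Summary, 7.9 and 7.11 on whether failed-fistula subjects may enter the 15- to 24-month follow-up.

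Cost: SAP wording and one extra table, with no new data collection.

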11.2.2 Subject Disposition

The number and percentage of subjects screened, screen failure, enrolled, treated, and completed will be summarized. Screen failure percentage is calculated from number of screened subjects and other percentages are calculated among number of enrolled subjects. A subject will be considered enrolled once they have signed the study patient

informed consent form. Subjects who discontinue from the study will be summarized with reason and listed by their primary reason for discontinuation.

11.2.3 Study Conduct

Protocol deviations from the investigation plan will be summarized by deviation type as well as total. Protocol deviations by investigational site will also be provided.

11.2.4 Analysis Samples

The primary and observational analysis samples will include all enrolled subjects with successful EchoMark LP implantation.

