NUMBER OF Clinical Sites	Up to 6 sites within in the United States will be evaluated, qualified, and selected for participation.										
PROCEDURE AND FOLLOW-UP:	All subjects that receive an EchoMark LP will be evaluated at the following time-points: • 15 days (+/- 7 days) • 30 days (+/- 7 days) • 60 days (+/- 15 days) • 90 days (+/- 15 days) • 120 days (+/- 15 days) • 150 days (+/- 15 days) • 150 days (e month) (+/- 15 days) • 12 Month (1 Year) (+/- 15 days) • 15 Months (+/- 15 days) • 18 Months (+/- 15 days) • 24 Months (+/- 15 days) • 24 Months (+/- 15 days) Except for the 180 day (6 month), 12 month (1 year), 15 Month, 18 Month, and 24 Months visits, each visit will include a physical exam, Duplex scan, EchoSure scan, and assessment for adverse events. The monthly EchoSure scans will be suspended after the 120-day (4 month) visit or once radiographic maturation is achieved, whichever is longer, but clinical follow-up and Duplex will continue per the above schedule. The 180-day (6-month) and 12 month (1 year)visits will include a physical examination, Duplex scan for patency, and an assessment for adverse events. The 15 Month, 18 Month, and 24 Month visits will include a physical examination, Duplex scan for patency, and an assessment for adverse events. The 15 Month, 18 Month, and 24 Month visits will include capture of medical history since the last visit, a duplex scan, information on any fluid collection observed on the Duplex scan, and an assessment for any adverse events. EchoSure scans will be completed by study personnel who do not have prior ultrasound training and are representative of non-expert users. Subjects that are consented but do not receive the EchoMark LP will be considered a screen failure, and can be replaced.										
Primary Endpoint	The primary safety and feasibility endpoints are as follows:										
	Primary Safety:										

	 Composite of new major device related adverse events (MAEs) at 30 days post EchoMark LP implantation, as adjudicated by the Clinical Events Committee (CEC), including: Device or procedure-related death Device related infection Device related interventions Device related hospitalizations Fistula failure Fistula rupture Aneurysm 							
	After the close of the final 90-day visit window, all evaluable subjects will be summarized and expansion to a pivotal trial will be requested under a new IDE.							
	Primary Feasibility (Technical Success):							

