4.2 Study Endpoints

4.2.1 Primary Safety Endpoints

Composite of new major device related adverse events (MAEs) at 30 days post EchoMark implantation, as adjudicated by the Clinical Events Committee (CEC) including:

- Device or procedure-related death
- Device related infection
- Device related interventions
- Device related hospitalizations
- Fistula failure
- Fistula rupture
- Aneurysm

After the close of the 90-day visit window, all evaluable subjects will be summarized and expansion to a pivotal trial will be requested under a new IDE.

4.2.2 Primary Feasibility (Technical Success):

Rate of Technical Success defined as the successful implantation of the EchoMark implant and the ability to determine blood flow, diameter and depth measurements using the EchoSure diagnostic ultrasound system from baseline to 4 months.

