11.2.7 Analysis of Primary Feasibility (Technical Success)

Definition of feasibility endpoints are described in Section 4.2.

For composite endpoints, i.e., technical success and implantation success, the number and percentage of subjects with success will be summarized. Descriptive statistics for components of each endpoint will also be provided.

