11.2.10 Handling of Missing Data

Data will only be absent from analyses of study outcomes in the event that they were not available for collection. In general, missing values in any of the endpoints will not be inputted when summarizing these endpoints using descriptive statistics.

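### Section 11.2.4 admits only successful implantations to the primary sample, so implantation success is 100% by construction, and 11.2.1 names a different set

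*Combined protocol and SAP*

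**What the plan says.** All references are to the combined protocol and SAP.

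- **Endpoint (4.2.2).** "Rate of Technical Success defined as the successful implantation of the EchoMark implant and the ability to determine blood flow, diameter and depth measurements" with EchoSure, from baseline to 4 months. There are two components: implantation and measurability.
- **Reporting (11.2.7).** For "technical success and implantation success, the number and percentage of subjects with success will be summarized", and descriptive statistics are promised for the components.
- **Sample (11.2.4).** "The primary and observational analysis samples will include all enrolled subjects with successful EchoMark LP implantation".
- **General rule (11.2.1).** "The primary analysis for all baseline characteristics and study outcomes will include all available data for all enrolled subjects".
- **Enrolment (11.2.2).** "A subject will be considered enrolled once they have signed the study patient" informed consent form; 7.3 also places enrolment at consent.
- **Missing data (11.2.10).** In general, "missing values in any of the endpoints will not be inputted when summarizing these endpoints".
- **No implant (synopsis).** "Subjects that are consented but do not receive the EchoMark LP will be considered a screen failure, and can be replaced". Section 6.6 agrees. Section 10.2 also allows replacement of consented subjects who do not get the study intervention.
- **Follow-up (synopsis).** "All subjects that receive an EchoMark LP will be evaluated at the following time-points"; no schedule is given for a subject whose placement failed and who has no device.
- **Roll-ins (5.1).** Up to 3 per site, outside the 20. Section 11.2.4 does not say whether they are in the sample.

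**The concern.** The event that admits a subject to the primary sample is the same event that the primary feasibility endpoint is meant to measure. A failed placement removes the subject from the denominator instead of counting as a failure. The implantation component cannot vary, and the composite is left measuring only whether EchoSure can take readings in subjects already implanted successfully.

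The plan does not settle the matter elsewhere. Section 11.2.1 gives a wider set for the same primary analysis, and nothing says which section prevails. The synopsis and 6.6 define a screen failure broadly enough to include an attempt that was abandoned with no device left in place.

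Technical success is the main feasibility result of a feasibility study, and its data feed the request for a pivotal trial (synopsis, 4.2.1). The same sample also serves primary safety. A subject with a device placed but judged unsuccessful is not a screen failure under 6.6, yet falls outside 11.2.4, so that subject's events would not enter the primary safety proportion.

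**Working it through.** **Figures in the plan.** There is no stated rate, threshold or power for this endpoint to reproduce; 11.1 gives up to 20 subjects and no null hypothesis. The intervals below use the exact binomial (Clopper-Pearson) method: lower limit = Beta quantile 0.025 with parameters (x, n−x+1), upper limit = Beta quantile 0.975 with (x+1, n−x). As a check on the method, 25/30 = 83.3% gives 65.3 to 94.4%, the interval printed in 3.5.

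**Algebra.** Let A = subjects attempted, S = successfully implanted, M = successfully implanted and measurable.

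- Under 11.2.4: implantation success = S/S = 100%; technical success = M/S.
- Among attempts: implantation success = S/A; technical success = M/A.
- Overstatement of technical success = (M/S)/(M/A) = A/S. This is 1.00 when no attempt fails.

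**Illustration, failed attempts replaced.** S = 20 (from the planned 20). The number of failed attempts and M = 18 are assumptions, since the documents give neither.

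| Failed attempts | Implantation success among attempts (95% CI) | Under 11.2.4 | Technical success among attempts | Under 11.2.4 | A/S |
|---|---|---|---|---|---|
| 1 | 20/21 = 95.2% (76.2-99.9) | 20/20 = 100% (83.2-100) | 18/21 = 85.7% | 18/20 = 90.0% | 1.05 |
| 2 | 20/22 = 90.9% (70.8-98.9) | 20/20 = 100% (83.2-100) | 18/22 = 81.8% | 18/20 = 90.0% | 1.10 |
| 3 | 20/23 = 87.0% (66.4-97.2) | 20/20 = 100% (83.2-100) | 18/23 = 78.3% | 18/20 = 90.0% | 1.15 |

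For the middle row, the technical-success intervals are 59.7 to 94.8% among attempts and 68.3 to 98.8% under 11.2.4.

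**Failed attempts not replaced.** With 20 attempted and 2 failed, implantation success is 18/20 = 90.0% (68.3-98.8) among attempts and 18/18 = 100% (81.5-100) under 11.2.4. If 2 of the 18 cannot be measured, technical success is 16/20 = 80.0% against 16/18 = 88.9%, a factor of 20/18 = 1.11.

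**What 100% would hide.** If the true implantation rate were 80%, 90% or 95% (assumed), the chance that 20 of 20 attempts succeed is 0.80^20 = 1.2%, 0.90^20 = 12.2% or 0.95^20 = 35.8%. Section 11.2.4 shows 100% every time.

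**The 11.2.1 set.** Suppose 20 implanted, 2 failed attempts and 3 subjects consented but never attempted (assumed). Implantation success is then 20/25 = 80.0% under 11.2.1, 20/22 = 90.9% among attempts and 20/20 = 100% under 11.2.4: three answers from one study.

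**The case against.** **Failures would be seen elsewhere.** A reader might infer that the study report could conceal implantation failures altogether. The documents do not support that. Section 11.2.2 tabulates screen failures and treated subjects, 9.5 requires device failures and explants to be reported to the sponsor within 24 hours, 7.4 records procedure success, and 11.2.1 promises subject listings. This mitigation is real but partial: the disposition table mixes failed attempts with subjects never attempted, and none of these sources enters the endpoint.

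**The bias may be zero.** This stands. Section 12.3.2 has the surgeon reposition the implant before securing it, and nothing in the documents shows that two or three failures in about 20 are likely. But a denominator set in advance should be able to register a failure, and the conflict between 11.2.1 and 11.2.4 remains either way.

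**Nothing is tested.** This also stands. Section 11.1 states no null hypothesis, no success threshold is given for technical success, and the pivotal request is not tied to a rate. A reader might infer a false claim of success; the documents support only an optimistic estimate.

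**Section 11.2.1 already repairs it.** One might argue that available-data analysis without imputation leaves roughly the attempted subjects. It does not: enrolment is at consent, and for a subject never attempted the absence of an implant is known, not missing.

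**An implanted set suits safety.** Largely fair. The composite is mainly device-related, and adding subjects who carry no device can dilute it: 2/20 = 10.0% would become 2/22 = 9.1% (assumed counts). That argues against one pooled attempted set for safety, but not for dropping a subject who has a device in place that was judged unsuccessful.

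**Conclusion.** The point holds. Under 11.2.4, implantation success is 100% by construction and technical success measures only readability among successful implants. Section 11.2.1 gives a different set, which wrongly includes subjects never attempted, and no rule says which applies.

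Technical success is overstated by attempted/successful: 1.05 to 1.15 for one to three failed attempts alongside 20 implants, and exactly 1.00 with none. In the illustration with 2 failed attempts and 2 unmeasurable subjects, 81.8% would be shown as 90.0%. All failure and measurability counts are assumptions.

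Two stronger conclusions do not follow. Technical success as a whole is not fixed at 100%, because measurement failure can still lower it. Nor is an overstatement certain, because it needs at least one failed attempt. The consequence is an optimistic descriptive estimate of the primary feasibility endpoint, which warrants correction because the change is cheap.

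**What to change.** 1. **11.2.4, feasibility sample.** Define the sample for technical and implantation success as all non-roll-in subjects in whom EchoMark LP placement was attempted. Count a failed placement as a failure even if the subject is replaced. Define 'attempted' and 'successful implantation' explicitly; the procedure-success item in 7.4 is itself undefined and cannot serve as the definition. Summarise roll-in subjects separately.
2. **11.2.4, comparison sample.** Keep an implanted sample for the EchoSure-duplex comparisons.
3. **11.2.1.** Refer to the 11.2.4 samples in place of all enrolled subjects.
4. **Synopsis, 6.6 and 10.2.** Limit screen failure to consented subjects with no placement attempt, and align the replacement rule in 10.2. Failed attempts may still be replaced, but they stay in the technical-success denominator.
5. **Primary safety (4.2.1, 11.2.6).** Include every subject in whom a device was placed, whether or not placement was judged successful. List events after failed attempts with no device left in place separately, without pooling them.

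The cost is wording in these sections and a reported rate that may be less favourable. If failed attempts are replaced, total attempts exceed 20; if not, each one leaves one fewer implanted subject for the comparisons.
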